This document gives a detailed statistical analysis plan (SAP) for the MifeMiso trial and should be read in conjunction with the current trial protocol. This SAP details the proposed analyses and presentation of the data for the main paper reporting the results for the MifeMiso trial. The results reported in these papers will follow the strategy set out here. Subsequent analyses of a more exploratory nature will not be bound by this strategy, though they are expected to follow the broad principles laid down here. The principles are not intended to curtail exploratory analysis (e.g. to decide cut-points for categorisation of continuous variables), nor to prohibit accepted practices (e.g. transformation of data prior to analysis), but they are intended to establish rules that will be followed, as closely as possible, when analysing and reporting data.

Any deviations from this SAP will be described and justified in the final report or publication of the trial (using a table as shown in Appendix A). The analysis will be carried out by an appropriately qualified statistician, who should ensure integrity of the data during their data cleaning processes.

2. Background and rationale

The background and rationale for the trial are outlined in detail in the protocol. In brief, miscarriage is common (20% of pregnancies; approximately 125,000 miscarriages per year in England).¹ It is associated with not only physical harm, such as excessive bleeding, infection, and uterine perforation during surgery, but also substantial psychological impact on women. Miscarriage is estimated to cost the NHS £81 million per year.² Management of miscarriage can be expectant (waiting for natural miscarriage), medical (with drugs) or surgical. A UK survey conducted by this study team has shown that 24% of women opt for medical management. However, there is uncertainty regarding the optimal drug regimens for medical management.³

Before the current NICE guideline CG154² was published in 2012, common practice was to use a combination of mifepristone and misoprostol (MifeMiso combination). The 2012 NICE guideline, however, recommended that misoprostol alone should be given to women having medical management². This recommendation was based on very limited evidence from one study of 115 women⁴, which found no difference between MifeMiso combination and misoprostol alone. Recognising the limited available evidence, the NICE guideline and HTA have called for a trial. In addition, the necessity of conducting such a trial was also supported by an unpublished patient survey (171/188 women thought worthwhile) and a clinician survey (120/152 of health professionals believe that a trial is necessary) at UK national level.

3. Trial objectives

Primary clinical objective: to test the hypothesis that treatment with mifepristone plus misoprostol is superior to misoprostol alone for the resolution of miscarriage within 7 days in women diagnosed with missed miscarriage by pelvic ultrasound scan in the first 13+6 weeks of pregnancy.

Key secondary objective:

To test the hypothesis that the addition of mifepristone reduces the need for surgical intervention to resolve the miscarriage.

Other secondary objectives:

1. To evaluate if the addition of mifepristone reduces the need for further doses of misoprostol.
2. To evaluate if the addition of mifepristone improves other clinical outcomes including surgical intervention up to and including 7 days post-randomisation and after 7 days post-randomisation, duration of bleeding, infection, negative pregnancy test at 21 days post-randomisation, time from randomisation to discharge from EPU care, side effects and complications.
3. To evaluate if the addition of mifepristone improves patient satisfaction
4. To assess the cost-effectiveness of the combination of mifepristone and misoprostol in the medical management of missed miscarriage.

Economic objectives: to assess the cost-effectiveness of the combination of mifepristone and misoprostol in the medical management of missed miscarriage based on an outcome of additional cost per additional successfully managed miscarriage and additional cost per additional quality-adjusted life-year (QALY). Using a model-based economic evaluation we will further explore the cost-effectiveness of the medical management of missed miscarriage, as explored in the proposed trial, with alternative management strategies, such as surgical and expectant, based on available secondary sources.

Mixed-method evaluation objectives: to explore the satisfaction of women who complete the trial protocol. The results of the satisfaction survey (CSQ-8) will act as a sampling frame to conduct semi-structured interviews to further investigate patient experiences and satisfaction with medical management of missed miscarriage.

4. Trial methods

4.1. Trial design

MifeMiso is a randomised, parallel group, double-blind, placebo-controlled multicentre study, with health economic and mixed-methods evaluation (see Appendix B for trial schema).

Potential participants will be recruited from Early Pregnancy Assessment Units (EPAUs) of participating centres.

Women diagnosed with missed miscarriage by pelvic ultrasound scan in the first 13+6 weeks of pregnancy that choose to have medical management of miscarriage will be randomised to mifepristone plus misoprostol (MifeMiso combination) or misoprostol alone.

It is anticipated that the trial will last for three years. Women will be followed up until final discharge which is usually after 21±2 days since randomisation. A semi-structured qualitative interview will be conducted on a subset of participants within 6 weeks of discharge.

4.2. Trial interventions

A single dose of oral mifepristone 200mg, followed by a single dose of vaginal, oral or sublingual misoprostol 800mcg 2 days later, will be compared with an oral placebo tablet followed by a single dose of vaginal, oral or sublingual misoprostol 800mcg 2 days later.

The 800mcg dose of misoprostol is justified by NICE guidance CG154.

4.3. Primary outcome measure

The primary outcome is failure to spontaneously pass the gestational sac within 7 days after randomisation. This will be assessed by pelvic ultrasonography where possible.

Some women will pass their gestational sac within 7 days post-randomisation and not attend hospital for pelvic ultrasonography at all or within 7 days. A Blinded Endpoint Review Committee (BERC) will assess participant data relevant to the primary outcome for women who have not received an ultrasound scan within 7 days post-randomisation (or have received a scan but scan results regarding passage of the gestational sac are not recorded). The BERC will assess whether sufficient additional information is available for the participant data to be included in the derivation of the primary outcome.

See Section 9.4 on data manipulations for how the primary outcome will be derived.

4.4. Secondary outcome measures

Secondary outcomes are as follows:

Key secondary outcome

- Surgical intervention to resolve the miscarriage (collected up to discharge from EPU care)

Other secondary outcomes

- Surgical intervention to resolve the miscarriage up to and including day 7 post-randomisation
- Surgical intervention to resolve the miscarriage after day 7 post-randomisation to discharge from EPU care
- Need for further doses of misoprostol up to day 7 post-randomisation
- Need for further doses of misoprostol up to discharge from EPU care
- Overall patient satisfaction score (measured using CSQ-8 questionnaire and collected upon discharge from EPU care)
- Patient quality of life (index value and overall health status measured using the EQ-5D-5L questionnaire and collected on date of randomisation, day 6-7 post-randomisation or day of follow-up USS if different to day 6-7 and day 21 +/- 2 days post-randomisation. If a woman obtains an initial positive pregnancy test result at day 21 +/- 2 days post-randomisation then a further EQ-5D-5L questionnaire is collected upon discharge from EPU care)
- Duration of bleeding reported by woman (days) (collected up to discharge from EPU care)

- Diagnosis of infection associated with miscarriage requiring outpatient antibiotic treatment (collected up to discharge from EPU care)
- Diagnosis of infection associated with miscarriage requiring inpatient antibiotic treatment (collected up to discharge from EPU care)
- Negative pregnancy test result 21 days (\pm 2 days) after randomisation
- Time from randomisation to discharge from EPU care (described using summary statistics only)

Safety outcomes

- Blood transfusion required (collected up to discharge from EPU care)
- Side effects (collected up to discharge from EPU care)
- Death (collected up to discharge from EPU care)
- Any serious complications (collected up to discharge from EPU care)

The analysis of the patient quality of life secondary outcome will be undertaken as part of the health economic analysis, and for which the analysis method is documented separately.

4.5. Timing of outcome assessments

The schedule of trial procedures and outcome assessments are given in Appendix C.

4.6. Randomisation

Randomisation will be performed on-line on a 1:1 ratio via a secure internet facility through a third party independent Integrated Trial Management System (MedSciNet Clinical Trial Framework). A "minimisation" procedure using a computer-based algorithm will be used to avoid chance imbalances in the following important variables:

- Maternal age (<30, \geq 30 years);
- Body mass index (<35, \geq 35 kg/m²);
- Previous parity (nulliparous, parous women);
- Gestational age (<70, \geq 70 days);
- Amount of bleeding (Pictorial Blood Assessment Chart score \leq 2, \geq 3);
- Randomising centre.

A 'random element' will be included in the minimisation algorithm, so that each woman has a probability (unspecified here) of being randomised to the opposite treatment that they would have otherwise received.

4.7. Sample size

We plan to randomise 710 women, 355 participants in each group. 670 women will need to be evaluated to detect a Minimally Important Difference (MID) of 10% reduction in the rate of failure to spontaneously pass the gestational sac within 7 days (i.e. from 25% to 15%), assuming 90% power and a type I error rate of 5%. However, assuming and adjusting for a worst case

scenario of 5% attrition, the total number of participants required will be 710. The 25% [95% CI: 23% to 27%] control group estimate is taken from our systematic review (unpublished data) and the 10% MID was the most popular selection from our health professional survey (41% of those surveyed). The estimate of the control group rate will be monitored throughout the recruitment period by the independent DMC to ascertain if any deviations from this assumption will impact on the sample size calculation.

4.8. Framework

The objective of the trial is to test the superiority of one intervention to another.

The null hypothesis is that there is no difference in failure to spontaneously pass the gestational sac within 7 days after randomisation between the intervention groups. The alternative hypothesis is that there is a difference between the groups.

4.9. Interim analyses and stopping guidance

A separate Data Monitoring Committee (DMC) reporting template will be drafted and agreed by the DMC including an agreement on which outcomes will be reported at interim analyses. The statistical methods stated in this SAP will be followed for the outcomes included in the DMC report, where possible.

Interim analyses of safety and efficacy for presentation to the independent DMC will take place during the study. The committee met once prior to the study commencement to agree the manner and timing of such analyses which will include the analysis of the primary and major secondary outcomes and full assessment of safety (serious adverse events). Criteria for stopping or modifying the study based on this information have been ratified by the DMC.

4.10. Pilot Progression Rules

Not Applicable

4.11. Timing of final analysis

The final analysis for the trial will occur once the last randomised woman is discharged following the resolution of miscarriage and the corresponding outcome data has been entered onto the trial database and validated as being ready for analysis. This is provided that the trial has not been stopped early for any reason (e.g. DMC advice or funding body request).

4.12. Timing of other analyses

Not applicable.

4.13. Trial comparisons

All references in this document to 'group' refer to mifepristone plus misoprostol (MifeMiso combination) or placebo plus misoprostol (misoprostol alone).

5. Statistical Principles

5.1. Confidence intervals and p-values

Estimates of treatment effects for all outcomes will be presented with 95% confidence intervals. Two-tailed p-values will be presented for the primary, key secondary and safety outcomes according to the strategy set out in section 5.2.

5.2. Adjustments for multiplicity

Multiple comparisons will be allowed for by following a hierarchical testing procedure. That is to say, the null hypothesis for the primary outcome will be tested first (at the 5% significance level) and if and only if the test is statistically significant will the key secondary outcome be tested. Otherwise, no further hypothesis testing will be performed. In order to assess any signal within specific organ groups, P-values will be presented for all safety outcomes unadjusted for multiple testing, as type I error rates (false positives) are less of a concern. Results from all other secondary outcomes will be treated as exploratory rather than confirmatory. No adjustments for multiple testing will be made for confidence intervals.

5.3. Analysis populations

All primary analyses (primary and secondary outcomes including safety outcomes) will be by intention-to-treat. Women will be analysed in the treatment group to which they were randomised, and all women shall be included whether or not they received the allocated treatment. This is to avoid any potential bias in the analysis.

5.4. Definition of adherence

The dispensing of the MifeMiso trial drug will be recorded in the pharmacy drug accountability log. Ingestion of the drug will be observed by a healthcare professional and documented in the patient's notes. This information will be collected on the trial specific data collection forms.

Adherence to allocated treatment will be defined as taking the allocated mifepristone/placebo on day 0 and subsequently misoprostol on day 2 unless the gestational sac has been passed before the scheduled time for misoprostol; in the latter case, the patient will be deemed to be adherent to the trial medication as long as the allocated mifepristone/placebo is taken on day 0.

5.5. Handling protocol deviations

A protocol deviation is defined as a failure to adhere to the protocol such as errors in applying the inclusion/exclusion criteria, the incorrect intervention being given, incorrect data being

collected or measured, follow-up visits outside the visit window or missed follow-up visits. We will apply a strict definition of the intention-to-treat-principle and will consider all randomised women as per the ITT population described in section 5.3 in the analysis, in some form, regardless of deviation from the protocol.⁵ This includes women who were randomised but later found to violate the inclusion or exclusion criteria. It does not include those women who have specifically requested to withdraw consent for the use of their data in the first instance; however these outcomes will be explored as per other missing responses.

5.6. Unblinding

The unblinding of the Trial Statistician to the intervention code will take place once the database is locked for final analysis, unless the DMC request that they review the interim data with knowledge of the intervention groups or the DMC request to be unblinded at an interim analysis.

6. Trial population

6.1. Recruitment

A flow diagram (recommended by CONSORT⁶) will be produced to describe the patient flow through each stage of the trial. This will include information on the number (with reasons) of losses to follow-up (drop-outs and withdrawals) over the course of the trial. A template for reporting is given in Appendix D1.

6.2. Baseline characteristics

Categorical data will be summarised by frequencies and percentages. Continuous data will be summarised by the number of participants, mean and standard deviation if deemed to be normally distributed, median and interquartile range if data appear skewed, and ranges if appropriate. Tests of statistical significance will not be undertaken, nor confidence intervals presented.⁷

The trial population will be tabulated as per Appendix D2. The following minimisation, demographic and other baseline variables will be described for the total population and for the two randomised groups separately: maternal age (years), BMI (kg/m²), previous parity, gestational age (days), amount of bleeding, ethnicity, medical history (current medication, diabetes, renal disease, cardiac disease, chronic hypertension, thyroid disease, cancer, other), and number of previous pregnancies (live birth, stillbirth, miscarriage, ectopic pregnancy, molar pregnancy, termination, pregnancy of unknown location).

7. Intervention(s)

7.1. Description of the interventions

A template for reporting information on the intervention(s) is given in Appendix D3.

7.2. Adherence to allocated intervention

A cross-tabulation of allocated treatment by the adherence categories stated in section 5.4 will be produced (proportions and percentages). A template for reporting adherence is given in Appendix D4.

8. Protocol deviations

Frequencies and percentages by group will be tabulated for the protocol deviations as per Appendix D5.

9. Analysis methods

Intervention groups will be compared using generalised estimating equations, or a similar method, to adjust for all covariates as specified in section 9.1, where possible.

9.1. Covariate adjustment

In the first instance, all estimates of treatment effects between groups for all outcomes will be adjusted for the minimisation variables as listed in Section 4.6, where maternal age, body mass index and gestational age will be treated as continuous fixed effects, parity and bleeding score as categorical fixed effects, and randomising centre will be included as a random effect.

If covariate adjustment is not possible (e.g. the model does not converge), centre will be dropped from the model in the first instance. If convergence of the model remains problematic, alternative models will be explored (e.g. Poisson regression). If this fails, unadjusted estimates will be produced, and it will be made clear in the final report why this occurred (e.g. not possible due to low event rate/lack of model convergence).

9.2. Distributional assumptions and outlying responses

Distributional assumptions (e.g. normality of regression residuals for continuous outcomes) will be assessed visually (via histograms for any continuous data) prior to analysis; although in the first instance the proposed primary method of estimation stated in this analysis plan will be followed. If responses are considered to be particularly skewed and/or distributional assumptions violated and potentially affecting the analysis then this will be examined through sensitivity analysis consisting of transformations or bootstrapping techniques. In the case of skewed distributions of continuous responses, this will consist of transformation of responses prior to analysis (log transformation in the first instance, although others may be used if deemed appropriate). If extreme values are apparent and considered to be affecting the integrity of the analysis, a sensitivity analysis consisting of removing the outlying response(s) and repeating the analysis will be performed. Output from these analyses, if performed, will be described and presented alongside the primary analysis with the excluded values clearly labelled. See section 9.10 for further details regarding sensitivity analyses.

9.3. Handling missing data

Every attempt will be made to collect full follow-up data on all study women and so it is anticipated that missing data will be minimal. Women with missing primary outcome data will not be included in the primary analysis in the first instance. This presents a risk of bias, and sensitivity analyses will be undertaken on the primary outcome measure⁸ to assess the possible impact of the risk and to make sure we are complying with the intention-to-treat principle.

The derivation of the primary outcome is based on information regarding passage of the gestational sac by USS at 6-7 days post randomisation, or self-report data reviewed by a Blinded End-point Review Committee if USS information is not available. A sensitivity analysis will be undertaken restricted to participants with available USS information only, to assess the robustness of the results that include clinical criteria for the primary outcome derivation.

See section 9.10 for further details regarding sensitivity analyses.

9.4. Data manipulations

The Trial Statistician will derive all responses from the raw data recorded in the database as follows:

Outcome measures

- **Failure to spontaneously pass the gestational sac within 7 days after randomisation**

Reported on PART E (treatment allocation) on the Randomisation Form and Section C (ultrasound scan) and Section E (surgical intervention) on the Outcomes Form by answering the following questions:

- a) Date of randomisation?
- b) Did the woman undergo scan(s) post-randomisation?
- c) If yes, was the sac passed?
- d) When was the date of scan?
- e) Did the woman require surgical intervention to resolve their miscarriage?
- f) When was the date of surgery?

The date of randomisation and date of scan will be used to calculate the number of days at which the scan was performed after randomisation. If the sac was passed as confirmed by an ultrasound scan, and it was passed within 7 days since randomisation and no surgical intervention was used to resolve the miscarriage before day 7 since randomisation, then the primary outcome will be coded as NO (i.e. not failed). If surgery for removing the sac was carried out within 7 days since randomisation, or the sac was not yet passed following the last scan which was performed at day 6-7 or beyond since randomisation then the primary outcome will be coded as YES (failed). If a woman did not undergo any scan after

randomisation and there was no surgery performed before day 7 since randomisation, or the last scan was undertaken within 5 days after randomisation and the sac was still present the primary outcome will be coded as MISSING, unless cases where the BERC unanimously decide that there is sufficient information available to confirm whether or not the primary outcome has been achieved and whether the sac was passed or not spontaneously by day 7 post-randomisation. The following questions from the Primary Outcome Review Form will be used to determine this:-

- A. Does the Committee unanimously agree that there is sufficient information available to confirm the primary outcome has been achieved?
- B. Does the Committee unanimously agree whether the sac was passed or not spontaneously by day 7 post-randomisation?
- C. Was the sac passed spontaneously by day 7 post-randomisation?
- D. Does the Committee unanimously agree on the date sac passed?
- E. Date sac passed

If A, B, C and D are all yes and E is before the date of surgery if surgery was required, then the primary outcome is NO (not failed).

If A and B are Yes and C is No, then the primary outcome is YES (failed).

If either A or B are No then C is not answered and the primary outcome remains MISSING.

- **Surgical intervention to resolve the miscarriage (collected up to discharge from EPU care)**

Reported on Section E (Surgical intervention) on the Outcomes form by answering the question "Did the woman require surgical intervention to resolve their miscarriage?" where the date of surgery is on or before the EPU discharge date.

- **Surgical intervention to resolve the miscarriage up to and including day 7 post-randomisation**

Reported on Section E (Surgical intervention) on the Outcomes form by answering the question "Did the woman require surgical intervention to resolve their miscarriage?" where the date of surgery is ≤ 7 days after the randomisation date.

- **Surgical intervention to resolve the miscarriage after day 7 post-randomisation to discharge from EPU care**

Reported on Section E (Surgical intervention) on the Outcomes form by answering the question "Did the woman require surgical intervention to resolve their miscarriage?" where the date of surgery is >7 days after the randomisation date.

- **Need for further doses of misoprostol up to day 7 post-randomisation**

Reported on Section B (misoprostol administration) on the Outcomes Form by answering the question "Was misoprostol taken by the woman?" and if yes, "Date taken". Any further doses of misoprostol within 7 days since randomisation will be identified by calculating the time difference:

Date of misoprostol taken - Date of randomisation.

At least one of the time differences calculated above should fall within the range of 2 to 6 days inclusive and should not be the first dose to warrant a YES to the outcome measure.

- **Need for further doses of misoprostol up to discharge from EPU care**

Reported on Section B (misoprostol administration) on the Outcomes Form by answering the question "Was misoprostol taken by the woman?" and if yes, "Date taken" Any further doses of misoprostol throughout the trial will be identified by calculating the time difference:

Date of misoprostol taken - Date of randomisation.

At least one of the time differences calculated above should be greater than or equal to 2, should be taken on or before the date of discharge from EPU care, and should not be the first dose to warrant a YES to the outcome measure.

- **Overall patient satisfaction score (measured using CSQ-8 questionnaire and collected upon discharge from EPU care)**

The outcome will be defined using a validated eight item client satisfaction questionnaire (CSQ-8)⁹. The CSQ-8 is a widely used instrument for assessing client satisfaction with health and human services, and has been used in previous trials of treatment for miscarriage¹⁰. The CSQ-8 is a brief, standardized measure of client satisfaction that is comprised of eight items. Each item asks respondents to provide their opinion and conclusions about services they have received. Each question is scored out of four. The overall score is produced by summing all item responses, with total scores ranging from 8-32 points, with higher scores indicating higher levels of satisfaction.

- **Duration of bleeding reported by woman (days) (collected up to discharge from EPU care)**

Reported on Section F (clinical outcomes until discharge) on the Outcomes form by answering "Date woman reported that bleeding started" and "Date woman reported that bleeding stopped", where days of bleeding will be computed from:

Date woman reported that bleeding stopped - Date woman reported that bleeding started.

This outcome will be treated as continuous.

- **Diagnosis of infection associated with miscarriage requiring outpatient antibiotic treatment (collected up to discharge from EPU care)**

Reported on Section F (clinical outcomes until discharge) on the Outcomes form by answering YES consecutively to the following three questions:

- a) Was the woman diagnosed with an infection that was associated with miscarriage?
- b) Were they treated as an outpatient?
- c) Was the woman prescribed antibiotics for the infection?

A binary outcome will be defined based on whether or not the above three conditions were satisfied simultaneously. If any are missing then the outcome will be coded as MISSING.

- **Diagnosis of infection associated with miscarriage requiring inpatient antibiotic treatment (collected up to discharge from EPU care)**

Reported on Section F (clinical outcomes until discharge) on the Outcomes Form by answering YES consecutively to the following three questions:

- a) Was the woman diagnosed with an infection that was associated with miscarriage?
- b) Were they treated as an inpatient?
- c) Was the woman prescribed antibiotics for the infection?

A binary outcome will be defined based on whether or not the above three conditions were satisfied simultaneously. If any are missing then the outcome will be coded as MISSING.

- **Negative pregnancy test result 21 days (\pm 2 days) after randomisation**

Reported on Section D (pregnancy test result) on the Outcomes form by answering YES to the question "Did the woman provide a pregnancy test result?" with a negative test result. A binary outcome will be defined based on whether the test result is positive or negative and a missing value will be taken if either the woman did not provide a pregnancy test result or the result is missing.

- **Time from randomisation to discharge from EPU care (described using summary statistics only)**

Reported on Section F (clinical outcomes until discharge) on the Outcomes form by answering the question "Date of final discharge from EPU care following a negative pregnancy test", and by calculating:

Date of final discharge from EPU care following a negative pregnancy test - Date of randomisation.

- **Blood transfusion required (collected up to discharge from EPU care)**

Reported on Section F (clinical outcomes until discharge) on the Outcomes form by answering the question "Did the woman require a blood transfusion from randomisation up until discharge from EPU care?" A binary variable will be defined. If a woman withdrew or was lost to follow up before being discharged, the binary outcome will take missing values.

- **Side effects (collected up to discharge from EPU care)**

Reported on the AE form AEs that are specified with a severity grade of 3, 4, or 5, from the first administration of trial treatment until discharge from EPU care. Events will be reported based on CTCAE category¹².

A binary outcome will be derived if a woman has at least one AE.

- **Death (collected up to discharge from EPU care)**

Reported on the SAE form.

- **Any serious complications (collected up to discharge from EPU care)**

Reported on the SAE form from the first administration of trial treatment until discharge from EPU care.

A binary outcome will be derived if a woman has at least one SAE.

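### Section 9.4 reads failure from the last scan, so a woman with the sac present at day 6-7 and gone on a later scan gets no primary-outcome code; sections 4.3 and 9.4 also define the BERC population differently

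*SAP*

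**What the plan says.** The endpoint is fixed at day 7. Section 4.3: "The primary outcome is failure to spontaneously pass the gestational sac within 7 days after randomisation". Section 9.3 describes the derivation as "based on information regarding passage of the gestational sac by USS at 6-7 days post randomisation", with BERC review where scan information is lacking.

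Section 9.4 then gives three codes.

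- **NO (not failed)** begins "If the sac was passed as confirmed by an ultrasound scan, and it was passed within 7 days since randomisation", and adds that there was no surgery to resolve the miscarriage before day 7.
- **YES (failed)** needs surgery within 7 days, "or the sac was not yet passed following the last scan which was performed at day 6-7 or beyond since randomisation".
- **MISSING** covers women with no scan and no surgery before day 7, "or the last scan was undertaken within 5 days after randomisation and the sac was still present the primary outcome will be coded as MISSING". The exception is where the BERC can settle the outcome unanimously.

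Section 4.3 gives the BERC's scope as review "for women who have not received an ultrasound scan within 7 days post-randomisation", or where a scan was done but the sac result was not recorded.

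Several scans per woman are provided for: the form asks "Did the woman undergo scan(s) post-randomisation". Follow-up runs well past day 7. Section 4.1: "Women will be followed up until final discharge which is usually after 21±2 days since randomisation".

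**The concern.** The endpoint asks about the sac at day 7, but the YES rule asks about the last scan, which may come at any time up to discharge. When a later scan overwrites the day 6-7 finding, an observed failure stops meeting the failure rule.

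The SAP then leaves the programmer to choose a code for a primary-endpoint event. If the woman is treated as missing, sections 9.3 and 9.5 exclude her from the primary analysis. The sensitivity analyses in section 9.10 do not repair this. The restricted analysis removes only BERC-determined outcomes. Multiple imputation runs only above 5% missing, and would replace an observed failure with a draw based on the minimisation variables.

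The loss falls only on failures. It therefore lowers the event rate, and it can distort the risk ratio if later documented passage is more common in one arm.

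**Working it through.** **1. The rules applied literally.** Scan dates come from the form; no surgery unless stated.

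| Scan history | YES | NO | MISSING | Result |
|---|---|---|---|---|
| Passed, day 6 | no | yes | no | NO, correct |
| Present day 6, passed day 7 | no | yes | no | NO, correct |
| Present day 7, no later scan | yes | no | no | YES, correct |
| Present day 4 only | no | no | yes | MISSING or BERC |
| Present day 7, passed day 14 | no | no | no | **no code** |
| Present day 7, surgery day 10, day-14 scan recorded as passed | no | no | no | **no code** |

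In the two uncoded rows the last scan shows no sac, so YES fails. Passage was not within 7 days, so NO fails. The last scan was not within 5 days, so MISSING fails. A scan with a recorded result exists within 7 days, so section 4.3 does not refer her to the BERC.

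**2. BERC scope in the two sections.**

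| History | Section 4.3 | Section 9.4 |
|---|---|---|
| Last scan by day 5, sac present | not referred (scanned within 7 days) | referred |
| First scan after day 7, sac passed | referred | not listed |

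**3. The plan's own sample size.** Inputs from section 4.7: 25% against 15%, 5% type I error, 90% power. Two-sided testing is from section 5.1 and 1:1 allocation from section 4.6.

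n per arm = [1.960 × √(2 × 0.20 × 0.80) + 1.282 × √(0.25 × 0.75 + 0.15 × 0.85)]² / 0.10² = 334.2, rounded up to 335, or 670 in total. This matches the SAP, and power at 335 per arm is 0.901. Allowing 5% attrition, 670/0.95 = 705.3, or 706 with equal arms, close to the planned 710.

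**4. Effect if the uncoded women are left out.** Let f be the share of day-7 failures with a later scan recording passage. The SAP gives no value, so a range is assumed. For an arm with true failure rate p:

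- analysed n = 335 × (1 − f·p)
- observed rate = p(1 − f)/(1 − f·p)
- women lost in total = 335 × f × (0.25 + 0.15) = 134f

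Power uses the two-proportion test with pooled null variance at the reduced n. With f equal in both arms:

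| f | Women lost | Control | Combination | Risk ratio | Power |
|---|---|---|---|---|---|
| 0 | 0 | 25.0% | 15.0% | 0.600 | 0.901 |
| 10% | 13 | 23.1% | 13.7% | 0.594 | 0.875 |
| 20% | 27 | 21.1% | 12.4% | 0.588 | 0.841 |
| 30% | 40 | 18.9% | 11.0% | 0.581 | 0.798 |
| 50% | 67 | 14.3% | 8.1% | 0.568 | 0.674 |

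With f unequal:

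- Control 20%, combination 40%: 0.20/0.95 = 0.2105 and 0.09/0.94 = 0.0957, risk ratio 0.455.
- Control 40%, combination 20%: 0.15/0.90 = 0.1667 and 0.12/0.97 = 0.1237, risk ratio 0.742.

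**5. Effect if the analyst codes them YES.** The rates stay at 25% and 15% and power at 0.901.

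**The case against.** The strongest reply is that the SAP leaves no doubt about what failure means. Sections 4.3 and 9.3 and the footnote to Appendix D6 all point to day 7, so a careful statistician would code the uncoded woman YES and nothing would be lost. That is a fair account of the intention. But section 9.4 is where the derivation is specified, and it does not say so.

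It is also fair that the frequency is unknown. Appendix C schedules no scan after day 6-7, and a woman without one is coded correctly. So f may be small, and the upper end of the range should not be read as a forecast.

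Three stronger readings are tempting but not supported.

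- A reader might infer that late passers are counted as successes. They are not: NO requires passage within 7 days, so power figures for that coding would describe something section 9.4 forbids.
- A reader might infer that the risk ratio must be biased. With equal f it moves only from 0.60 to 0.58 at f = 30%. Material bias needs f to differ by arm, and the documents give no figure for that.
- A reader might infer that a woman first scanned after day 7 with the sac gone has no route to a code, or that late scans count only when they show failure. Section 4.3 sends her to the BERC, whose answers can give NO. The asymmetry is also logical: a sac present after day 7 proves failure at day 7, while a sac absent then does not show when it passed. What remains is a mismatch between 4.3 and 9.4.

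**Conclusion.** The point holds in a limited form. Section 9.4 gives no code, and section 4.3 no BERC route, to a woman with the sac present at day 6-7 and a later scan recorded as passed, although the SAP's own definition makes her a failure. The two sections also disagree on whom the BERC reviews.

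The consequence depends on how the analyst fills the gap. Coding these women YES costs nothing. Leaving them out, with f equal in both arms, takes power from 90% to about 87.5%, 84%, 80% and 67% at f = 10%, 20%, 30% and 50%, with little change in the risk ratio. With f at 20% in one arm and 40% in the other, 0.60 becomes 0.455 or 0.742. All of these figures rest on assumed values of f and on the planned 25% and 15%.

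One neighbouring case is not clear-cut. A woman with the sac present on day 6 and gone on day 8 may have passed it on day 7, so she is not a certain failure.

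The sample size itself reproduces; the defect is in the coding rule. Because it concerns the primary endpoint, it should be settled before the database is locked and the trial statistician is unblinded.

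**What to change.** Rewrite the derivation in section 9.4 as follows.

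- **YES**, in addition to the surgery clause: the sac is present on the day 6-7 scan and no scan by day 7 shows it passed, or any scan after day 7 shows it present. Either applies whatever later scans show.
- **Surgery conditions** for YES and NO: leave as they stand.
- **BERC referral**: women with no scan, women whose last scan was by day 5 with the sac present, and women with no day 6-7 scan whose first later scan shows passage. Keep the group in section 4.3 whose sac result was not recorded. If the BERC cannot decide, the code is MISSING.
- **Boundary case**: say explicitly whether sac present on day 6 with passage on a scan just after day 7 is YES or goes to the BERC.
- Check that every scan history receives exactly one code, and restate the BERC scope in section 4.3 to match.

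The cost is SAP wording and derivation code. Section 9.4 shows that scan dates, sac results and surgery dates are already collected. Newly referred women would need BERC review while it is still blinded.
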